4.5 Concomitant Therapy

It is expected that participants in this study will receive numerous concomitant therapies unrelated to the research interests of this study. Only the study treatment and pain control treatments will be analyzed to determine the study outcomes. Exposure to vincristine (dose preceding NP event, as well as total cumulative dose) will be recorded.

4.6 Supportive Care

Morphine is prescribed for use as needed for breakthrough pain. See sections 4.1 and 4.3.

5.0 DRUG/DEVICE/BIOLOGIC AGENT INFORMATION

5.1 GABAPENTIN (Neurontin®)

Source and Pharmacology: Gabapentin is a white to off-white crystalline solid that is freely soluble in water. Its mechanism of action in preventing seizures is not known. Gabapentin is not appreciably metabolized in humans; pharmacological effects are from the activity of the parent compound. It is eliminated unchanged in the urine. Patients with renal impairment should have dosage adjustments. Higher doses are less bioavailable than lower doses after oral administration, but across the recommended dose range of 300 mg to 600 mg T.I.D., the bioavailability

is approximately 60%. Administration with food has little effect on absorption of gabapentin.

Formulation and Stability: Gabapentin is supplied as 100 mg, 300 mg, and 400 mg capsules, and as an oral solution containing 50 mg/ml. The tablets and capsules can be stored at room temperature, and the oral solution must be refrigerated.

Toxicity: Patients 3 – 12 years old treated with gabapentin for epilepsy reported the following central nervous system related adverse events: emotional lability, hostility, thought disorder and hyperkinesia in addition to CNS depression (dizziness, somnolence, fatigue, ataxia, and nystagmus). In placebo controlled trials of gabapentin in children taking other antiepileptic drugs, the following were also seen at higher frequency in the treatment group than the placebo group: viral infection, bronchitis, pharyngitis, rhinitis, respiratory infection, coughing, otitis media, fever, nausea and/or vomiting, diarrhea, depression, headache, diplopia, blurred vision, nervousness, seizures, pruritus, dyspepsia, constipation, weight gain, anorexia, leukopenia, back pain, and peripheral edema.

Supplier: Commercially available

Dosage and Route of Administration: Participants randomized to the active treatment arm will receive gabapentin 20mg/kg/day PO divided into 3 doses and rounded to the nearest 100 mg for capsules and 10 mg for liquid preparation.

Do not administer within two hours of aluminum or magnesium containing antacids. Abrupt withdrawal of gabapentin therapy may precipitate seizures.

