6.2 Evaluations During Therapy

Participants will be evaluated daily by pain intensity assessments, using age appropriate tools, until completion of the study treatment. The maximum duration of the study cannot exceed 21 days. The pain assessment tools are the FLACC scale (0-10) for participants younger than years of age or other children who cannot self report²³, the Faces Pain Scale-Revised (FPS-R) (0-10) for ages 4-7²⁴, and the numeric scale (0-10) for ages older than 7^{25,26}. This assessment can be obtained during a clinical evaluation or by phone interview, if a clinical visit is not feasible.

Additional data will be obtained regarding location and descriptors of pain (daily) and the daily dose of morphine used during the study.

The GFR of participants will be monitored at least weekly while on study, using clinically obtained creatinine levels to estimate GFR using the Schwartz equation^{21,22}. Patients who develop renal impairment (estimated GFR < 60ml/min/1.73m²) will be taken off therapy.

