6.4 Off-Study Evaluations

Patients will be off study when the patient has completed the study treatment and applicable pain assessments have been collected. If pain symptoms persist at the completion of the study, the patient will continue to be treated as needed, with gabapentin and/or morphine, either by the pain team or the leukemia team, but no additional data will be collected for this study.

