8.2 Off-therapy criteria

- 8.2.1 Development of unacceptable toxicity during treatment
- 8.2.2 Development of renal impairment, defined as GFR less than 60ml/min/1.73m² as estimated by the Schwartz equation^{21,22}.**
- 8.2.3 Refusal of therapy
- 8.2.4 Unblinding of participant or study team to participant's treatment assignment (see section 9.3)**

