APPENDIX I
EXAMPLE OF A SCHEDULE OF EVALUATIONS:

Upon confirmation of eligibility (any time between days 1 and 7 after qualifying vincristine dose, see section 3.0):

- Informed consent discussion
- Enrollment data obtained by study team
- Baseline pain assessment by study team
- Participant receives prescription for morphine PRN (see section 4.2)
- Participant is randomized and begins study drug (see section 4.1)

Enrollment through Day 21

- Daily pain assessment by study team
- Daily AE assessment by study team
- Refill morphine if needed
- Patient/family education regarding study drug

Day 21

- Complete last dose of study drug
- Complete last daily pain assessment and AE assessment
- Refer persistent pain to pain team or primary clinic for treatment as clinically indicated

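### The plan warns of seizures on abrupt gabapentin withdrawal but schedules no adverse event question after the planned last dose; one blinded contact would add it (minor)

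*Combined protocol and SAP*

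**What the plan says.** - **Hazard.** The drug information in Section 5.1 states: "Abrupt withdrawal of gabapentin therapy may precipitate seizures".
- **Schedule.** From enrollment through Day 21, Appendix I lists "Daily AE assessment by study team". Under Day 21 it lists both "Complete last dose of study drug" and "Complete last daily pain assessment and AE assessment". In Appendix II the study-drug and AE columns also run to Day 21, and there is no later row.
- **End of study.** Section 6.4: "Patients will be off study when the patient has completed the study treatment and applicable pain assessments have been collected". For patients whose pain persists, who may receive gabapentin or morphine as clinical care, it adds that "no additional data will be collected for this study". Section 6.2 sets a ceiling: "The maximum duration of the study cannot exceed 21 days".
- **Stopping the drug.** The only stepwise reduction in the readable text is 5 to 10 mg/kg/day for side effects (Section 4.3). Section 4.1 leaves changes in dose, duration and discontinuation to the study team.
- **Early stops.** Section 8.2 lists reasons for going off therapy, among them "Development of unacceptable toxicity during treatment". These are separate from the off-study reasons in Section 8.1.
- **Reporting.** Sections 9.1.1 and 9.2 set reporting times that run from discovery of an event, with no end date. Events that the principal investigator judges unrelated go through the Total XVI procedures (9.1.1). The study database takes study-related events (9.1.2). The synopsis promises more broadly that any adverse event will be recorded and reported.

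**The concern.** A withdrawal effect can appear only after the drug stops. The plan names one for a drug given to children, yet its scheduled AE questions end on the day of the planned last dose. After that, the study learns of an event only if someone happens to report it. An event also reaches the study database only if it is judged study-related, and that judgement would normally be made without knowing whether the child had just stopped gabapentin or placebo.

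What is at stake is the safety record after treatment, and with it the chance to compare that period between the arms. The morphine and pain-score comparisons are not affected.

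**Working it through.** The plan gives no figure to reproduce here. The check compares the last dose with the last scheduled AE question.

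**1. Planned completion**
- Planned last dose: Day 21 (Appendix I; Appendix II agrees).
- Last scheduled AE assessment: Day 21 (same sources).
- Scheduled AE observation after the last dose = 21 − 21 = **0 days**.

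**2. Does a delayed course change this?** The synopsis continues study drug until 7 days after the second vincristine dose. Section 4.1 dispenses a supply for not more than 21 days, and Section 11.1 foresees delayed vincristine. The actual last dose may therefore not fall on Day 21 counted from the qualifying dose. The gap stays, because 6.2 runs daily evaluation only until study treatment is complete and 6.4 then closes participation. The 0 days thus attach to the last dose, whatever its calendar day.

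**3. Early stoppers.** Appendix I, which is titled as an example, could be read as continuing daily AE assessment to Day 21 after an early stop. Against that, the synopsis, 6.2 and 7.1 tie daily data collection to study treatment. The documents do not settle the matter, so no day count is given for this group. A contact tied to each patient's own last dose works under either reading.

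**4. Is there room for a contact under the current limits?** With on-time vincristine, a participant who starts on Day s has 21 − s + 1 treatment days.
- s = 1: 21 days, leaving 21 − 21 = 0 under the 21-day maximum.
- s = 7: 15 days, leaving 21 − 15 = 6 if the maximum is counted from the patient's own start.

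A Day 1 starter cannot be contacted after the last dose unless 6.2 is amended. The same counts show that the team already makes 15 to 21 daily contacts per completer.

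**5. What one contact adds.** A contact k days after the last dose gives k days of observation instead of 0. The documents give no k. If k is assumed to be 2 to 7, the cover is 2 to 7 days.

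**6. What it cannot add.** If n gabapentin participants are asked and none reports an event, the one-sided 95% upper bound on the event rate is 1 − 0.05^(1/n): 9.5% for n = 30 and 7.2% for n = 40. This holds for any trial of that size and assumes that all n stopped gabapentin. It describes the limit of the remedy and says nothing about the risk in this trial.

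**The case against.** **The hazard may not apply.** The warning is one general line of drug information. The pediatric toxicity data beside it come from children treated for epilepsy or taking other antiepileptic drugs. This trial gives 20 mg/kg/day for at most 21 days, whereas Section 2.2 describes titration to 50 to 70 mg/kg/day. The documents give no event rate and do not say how far the warning carries over. This stands, and it is why the point is minor.

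**Events would surface anyway.** These children are under active leukemia treatment, persisting pain is handed to the pain or leukemia team, and reporting has no end date. A seizure would probably be noticed. This largely stands. A reader might infer that a seizure after Day 21 would go unreported; the documents do not support that, because a discovered event has a route whichever way it is attributed. What remains is that nobody is scheduled to ask.

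**Some patients do not stop.** Section 6.4 allows clinical gabapentin if pain persists. The number is unstated. Children whose pain has resolved are the ones who simply stop.

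**The contact prevents nothing.** True. It improves what the trial observes and does not make stopping safer. A reader might infer that the plan should mandate a taper. The documents do not establish that need at this dose and duration, Section 4.1 leaves discontinuation with the study team, and the treatment-plan figure is not readable, so a taper shown there cannot be ruled out.

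**Conclusion.** The concern holds as a minor gap in safety ascertainment. After the planned last dose the plan schedules 0 days of AE observation for a hazard that it names itself. The gap affects about 30 gabapentin participants, or 40 if 80 enroll and split equally, less an unstated number who go on to clinical gabapentin.

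The conclusion rests on the readable text of Sections 5.1, 6.2 and 6.4 and Appendices I and II. It needs no assumption about how often withdrawal events occur. It does not show that participants face an unmanaged risk or that events would be lost. It shows that an absence of reports after treatment would rest on spontaneous discovery and not on a question put to everyone.

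**What to change.** 1. Add to Appendices I and II one AE contact, by phone if needed, a few days after each participant's actual last dose of study drug, on a day set by the sponsor. It should be identical in both arms and blinded. It applies to completers and early stoppers, but not to those who withdraw from the study.
2. Ask about seizures, other new symptoms, and whether clinical gabapentin was started. Record the answers in the study database regardless of attribution.
3. Amend 6.4 so that off-study status follows this contact.
4. Amend 6.2 so that the 21-day limit applies to study treatment.

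**Cost.** At most one call per participant (60 to 80 in all), on top of the daily contacts already made; 6.2 already accepts the phone for pain assessment. Participants stay on study a few days longer. Sample size, blinding and the primary analysis are unchanged. A reported event could still have other causes, and the placebo arm helps to judge that. Tapering stays a clinical decision.

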5.2 PLACEBO

Placebo capsules contain microcrystalline cellulose as filler to a weight equivalent to the active agent. The capsules should be stored at room temperature in the pack provided. The expiration date will be listed on the product label. Placebo capsules will be compounded for patients by Regel PharmaLab (a local compounding pharmacy) to match the active capsules in appearance as closely as possible. St Jude pharmacy will dispense the capsules and keep accountability records as per randomized assignment.

Placebo syrup will be compounded with simple syrup diluted with normal saline with flavoring added. The solution should be stored in the refrigerator. The expiration date will be listed on the product label. Placebo syrup will be prepared by the St. Jude Children's Research Hospital Pharmacy for distribution to the patient.

To allow for the study team and participants to remain blinded to the treatment assignment, the study drug will be labeled by the pharmacy as “TINALL study treatment (gabapentin vs. placebo)” followed by applicable dose and administration instructions.

6.0 REQUIRED EVALUATIONS, TESTS, AND OBSERVATIONS

Subsections of 6.0 are outlined in tabular form in Appendix I.

6.1 Pre-Study Evaluations

The eligibility depends on establishing the initial diagnosis of NP/PN related to vincristine; this is a clinical diagnosis that is documented in the medical record and does not require any additional tests. Documentation of NP/PN made in the medical record by any St. Jude clinician will serve as the source for this diagnosis and for determining eligibility.

Female participants of childbearing potential must have documentation of a negative pregnancy test not older than 7 days at the time of enrollment; if this is not available, the study team will order the test to be performed and reviewed prior to starting study drug.

Clinically obtained creatinine levels will be used to estimate the GFR using the Schwartz equation^{21,22}. Patients with estimated GFR <60ml/min/1.73m² will not be enrolled.

6.2 Evaluations During Therapy

Participants will be evaluated daily by pain intensity assessments, using age appropriate tools, until completion of the study treatment. The maximum duration of the study cannot exceed 21 days. The pain assessment tools are the FLACC scale (0-10) for participants younger than years of age or other children who cannot self report²³, the Faces Pain Scale-Revised (FPS-R) (0-10) for ages 4-7²⁴, and the numeric scale (0-10) for ages older than 7^{25,26}. This assessment can be obtained during a clinical evaluation or by phone interview, if a clinical visit is not feasible.

Additional data will be obtained regarding location and descriptors of pain (daily) and the daily dose of morphine used during the study.

The GFR of participants will be monitored at least weekly while on study, using clinically obtained creatinine levels to estimate GFR using the Schwartz equation^{21,22}. Patients who develop renal impairment (estimated GFR < 60ml/min/1.73m²) will be taken off therapy.

6.3 Response Evaluations

Evaluations will continue as described in section 6.2.

6.4 Off-Study Evaluations

Patients will be off study when the patient has completed the study treatment and applicable pain assessments have been collected. If pain symptoms persist at the completion of the study, the patient will continue to be treated as needed, with gabapentin and/or morphine, either by the pain team or the leukemia team, but no additional data will be collected for this study.

6.5 Long-Term Follow-up Evaluations

This study will not evaluate NP events or long term results beyond the off study evaluation.

Participants will be notified of their treatment assignment (gabapentin or placebo) after the completion of data collection for the last participant enrolled. Notification will be performed by a member of the study team in person (when feasible) or by letter at the earliest convenience of the study team and documented in the study files.

7.0 EVALUATION CRITERIA

7.1 Response Criteria

The response to therapy will be measured by pain intensity scores and daily use of morphine doses for breakthrough pain as described in the study objectives. Daily assessments will continue during treatment with the study drug (gabapentin or placebo) irrespective of patient response to study treatment.

7.2 Toxicity Evaluation Criteria

Participants who experience unacceptable side effects will have dosage adjustments or will be removed from the study (see section 4.4). The decision to adjust the study treatment dose or to discontinue study treatment will be made by the PI and in the context of the participant's clinical situation.

8.0 CRITERIA FOR REMOVAL FROM PROTOCOL THERAPY AND OFF-STUDY CRITERIA

8.1 Off-study criteria

- 8.1.1 Completion of study therapy and assessments
- 8.1.2 Death
- 8.1.2 Lost to follow-up
- 8.1.3 Request of the Patient/Parent
- 8.1.4 Discretion of the Study PI, such as the following
 - The researcher decides that continuing in the study would be harmful
 - New information is learned that a better treatment is available, or that the study is not in the participant's best interest

8.2 Off-therapy criteria

- 8.2.1 Development of unacceptable toxicity during treatment
- 8.2.2 Development of renal impairment, defined as GFR less than 60ml/min/1.73m² as estimated by the Schwartz equation^{21,22}.**
- 8.2.3 Refusal of therapy
- 8.2.4 Unblinding of participant or study team to participant's treatment assignment (see section 9.3)**

9.0 SAFETY AND ADVERSE EVENT REPORTING REQUIREMENTS

9.1 Reporting Serious Adverse Events

9.1.1 IRB Notification by Investigator

Adverse events (AEs) will be graded according to the CTCAE version 4.0. All study-related anticipated AEs of grade 3 or higher will be reported to the IRB via institutional reporting mechanisms. Those AEs grade 2 or below will be reported to the IRB at the time of continuing review. All serious, related (or possibly related), and unexpected AEs of all grades will be reported to the IRB within 48 hours of discovery of the event. Others will be reported within 10 working days of discovery of the event.

Adverse events determined by the PI to be unrelated to the study treatment will be reported by the procedures outlined in the primary treatment protocol (Total XVI).

9.1.2 Recording Adverse Events and Serious Adverse Events

Adverse events will be submitted by a member of the study team to the IRB using the existing institutional online reporting mechanisms. All study-related AEs will be collected in the database, regardless of their grade.

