Patients with ALL on Total XVI or "as per TOTXVI" who experience NP/PN after specific doses of vincristine are eligible to enroll in the study as soon as the diagnosis of NP/PN related to VCR is established. The qualifying doses of vincristine have been selected because they fall in the schedule of weekly vincristine doses as per Total XVI, and 2 additional weekly vincristine doses are anticipated according to the protocol. Participants will be randomized to receive gabapentin or placebo upon enrollment. Morphine will be available to both groups as needed for pain at any time on the study. At the time of enrollment, and daily thereafter until completion of the study drug, data will be collected for pain assessment, and the daily dose of oral morphine used will be collected. Data regarding the pain type, quality, and location, as well as treatments used to manage pain will be assessed on a daily basis for the diagnostic event and for the period following the next two administrations of VCR treated with the study drug.

Objectives:

Primary Objective:

To assess the analgesic efficacy of gabapentin in controlling VCR-related NP/PN in participants with ALL, by comparing the morphine daily dose (mg/kg/day) used to control NP/PN as a primary or a rescue regimen in the gabapentin vs. placebo groups.

Secondary Objective:

To compare the pain scores in the gabapentin and placebo groups as recorded by pain score right now and pain score average for previous 24 hours.

Responsible Investigator: [name]

Statistician: [name].

Estimated date for completion of data collection: December 2015

TINALL - Therapeutic Interventions for Peripheral Neuropathy/Neuropathic Pain Induced by Vincristine Treatment for Childhood ALL on Total XVI Protocol

Hypotheses/Estimates: The hypothesis is that treatment with gabapentin has better analgesic efficacy than placebo in the treatment of VCR-related NP/PN. Based on the current enrollment on the Total XVI protocol, the projected enrollment, the incidence of NP/PN of 34.9% as determined in our previous study of NP/PN associated with the Total XV protocol, we estimate that 60 study participants will be eligible to enroll in this study during the duration of the Total XVI study. To achieve a total of 60 evaluable patients, up to 80 participants may be enrolled.

Criteria for Evaluation:

Safety: Any adverse events will be recorded and reported.

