10.0 DATA COLLECTION, STUDY MONITORING, AND CONFIDENTIALITY

10.1 Data Collection

A member of the TINALL study team will complete documentation in MILLI for each study encounter (“anesthesia research note”). Data will then be entered into a secure database, which serves as the electronic case report forms (eCRFs). Records from the study which identify the study participant will be kept confidential in a secured area.

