11.0 STATISTICAL CONSIDERATIONS

11.1 Primary Objective

This study has the following single primary objective:

To assess the analgesic efficacy of gabapentin in controlling VCR-related NP/PN in participants with ALL, as reflected by the morphine daily dose (mg/kg/day) used to control NP/PN as a primary or a rescue regimen, and by daily pain scores in the gabapentin vs. placebo groups.

Accrual: The eligibility criteria requires that a patient can be enrolled in this study only if a VCR-induced NP not previously treated by gabapentin occurred after vincristine doses administered at the following time points: Induction Week 1 ± 3 days, Induction week 2 ± 3 days, Continuation Week 7 (Re-induction I) ± 3 days or Week 17 (Re-induction II) ± 3 days of Continuation. A review of Total XVI or “as per TOTXVI” patients up to the date of this protocol development showed that respectively 33, 29, 5, and 1 patient satisfied the condition at the time points. A review of Total XV showed a similar pattern. Thus we expect to enroll for this study at least 60 patients in the remainder of Total XVI or “as per TOTXVI. We will enroll and randomize all eligible and consented patients in the remainder of Total XVI or “as per TOTXVI”. To achieve a total of 60 evaluable patients, up to 80 participants may be enrolled.

Study Design: Placebo-controlled, randomized Phase-II trial. Sixty (60) participants will be randomized into the treatment (gabapentin) and the placebo group, with 30 patients per group.

Analysis: For each subject a pre-treatment (baseline) pain score will be obtained from the leukemia clinic. This score serves as the baseline level of pain and is used in stratified randomization (see below); and if necessary, as a covariate in modeling the daily morphine dosage used for pain control. The daily morphine dosage will be modeled as longitudinal observations with treatment (gabapentin vs. placebo) group, and if necessary, other clinical factors such as age category for pain assessment (0-3yr, 4-7yr, >7yr), baseline pain score, and ALL risk classification, as explanatory factors, using repeated measure linear models.

Multiple test adjustment will not be made. Participants **whose doses of vincristine are delayed or those who are taken off study drug** will be included in the analysis according to “intent to treat”.

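### The summary says any adverse event is recorded, but the only database rule covers study-related events, so a by-arm safety summary would depend on attribution

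*Combined protocol and SAP*

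**What the plan says.** Four places set the scope of adverse event (AE) data.

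- **Protocol summary, Criteria for Evaluation.** The safety line reads "Any adverse events will be recorded and reported". It carries no relatedness condition.
- **Section 9.1.2, on recording AEs.** "All study-related AEs will be collected in the database, regardless of their grade". This removes any grade limit and mentions study-related events alone.
- **Section 9.1.1, on IRB notification.** "Adverse events determined by the PI to be unrelated to the study treatment will be reported by the procedures outlined" in the Total XVI protocol. The PI makes the judgement.
- **Appendix I.** From enrollment through Day 21 it lists "Daily AE assessment by study team". Appendix II has a matching AE column for each study day.

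Section 10.1 adds that each study encounter is documented in a research note and that data then go to the database serving as the eCRF. It does not say which AEs are entered. Section 11 contains no safety analysis.

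**The concern.** A placebo arm allows the excess of events on gabapentin to be estimated without deciding the cause of each one. That works only if events are kept whatever their presumed cause. If relatedness is decided before data entry, the comparison takes on the quality of that decision.

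The decision is hard in this population. Open-label morphine is available to everyone (section 4.2), all participants receive vincristine, and section 4.5 notes: "It is expected that participants in this study will receive numerous concomitant therapies unrelated to the research interests of this study". Section 5.1 lists somnolence, dizziness, fatigue, nausea and/or vomiting, constipation and leukopenia among gabapentin's effects. Several of these could reasonably be put down to morphine or chemotherapy. Sections 4.3 and 4.4 name sedation/drowsiness as gabapentin's most common side effect, so an event the protocol itself highlights is among those exposed to the problem.

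**Working it through.** **Step 1: compare the texts.**

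| Place | Events covered | Destination |
|---|---|---|
| Summary | Any AE | Not stated |
| 9.1.1 | AEs the PI judges unrelated | Total XVI procedures |
| 9.1.2 | Study-related AEs, any grade | Trial database |
| 10.1 | Not stated | Research note, then database |
| Appendices I and II | AEs assessed daily, no relatedness condition | Not stated |

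The word *only* does not appear in 9.1.2. The narrower reading is an inference: 9.1.2 lifts the grade limit and leaves relatedness as the sole condition, 9.1.1 sends the remaining events elsewhere, and no other section brings them back. The inference is well supported but it is not explicit. All of this is current text.

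**Step 2: illustrate what a relatedness filter could do.** The documents give no AE rate, no safety hypothesis and no significance level for safety, so there is no figure of the plan's own to reproduce. Inputs:

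- n = 30 per arm, from section 11.1 ("with 30 patients per group").
- Assumed: 20% of placebo and 45% of gabapentin participants have sedation.
- Assumed: one-sided 0.05, critical value 1.645.
- Assumed: a fraction f of affected participants in each arm has the event judged unrelated and therefore not entered.

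Formula: h = 2·arcsin√p₁ − 2·arcsin√p₀, and power = Φ(h·√(n/2) − 1.645), with √(30/2) = 3.873.

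With nothing removed, h = 0.543, so h·√(n/2) = 2.104 and power = Φ(0.459) = 0.68.

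| f | Placebo v gabapentin in database | Difference (points) | h | Power |
|---|---|---|---|---|
| 0 | 20% v 45% | 25 | 0.543 | 0.68 |
| 10% | 18% v 40.5% | 22.5 | 0.503 | 0.62 |
| 20% | 16% v 36% | 20 | 0.464 | 0.56 |
| 50% | 10% v 22.5% | 12.5 | 0.345 | 0.38 |

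Equal proportional loss leaves the ratio at 45/20 = 22.5/10 = 2.25. The absolute difference and the number of events fall.

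**Step 3: change the assumption about which events are lost.** Suppose the filter removed mainly background events, say 10 percentage points from each arm. The database would show 10% v 35%, h = 0.623, and power = Φ(2.411 − 1.645) = 0.78. The direction of the effect therefore depends on which events are removed, and the documents do not settle that.

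**The case against.** The strongest reply is that 9.1.2 sets a minimum. It says that study-related events will be entered and does not exclude others, and section 10.1 describes data entry without any relatedness filter. The sentence in 9.1.1 stands under IRB notification and concerns reporting. The summary line does not say where events are recorded, so research notes plus the two reporting routes could satisfy it. This stands as far as the word *only* goes. It does not supply a rule that puts unrelated events in the database.

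A reader might infer that events judged unrelated are lost for good. The documents do not support that. Study encounters are documented in notes, and Total XVI has its own reporting, so partial recovery is possible. The Total XVI thresholds are not in these documents, and the plan makes no provision for using either source.

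A reader might also infer bias between the arms. Section 5.2 describes labelling "To allow for the study team and participants to remain blinded to the treatment assignment", so attribution should not differ by arm in principle, although sedation could weaken the blind. An assessor who expects sedation from the study drug may also be inclined to call it at least possibly related, which would make the loss small for that event.

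Finally, safety is neither a primary nor a secondary objective, and section 11 proposes no safety test. The power figures thus refer to a comparison the trial did not plan. In an add-on study, leaving unrelated events to the parent protocol is a defensible way to avoid duplicate capture. These points limit how serious the matter is. They do not remove the mismatch in scope, nor the advantage of a comparison free of attribution.

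**Conclusion.** The point holds in a limited form. The summary, 9.1.1 and 9.1.2 do not give one consistent scope, and nothing in the protocol places AEs judged unrelated in the trial database. On that reading, any by-arm safety summary from the database would rest on blinded attribution, for symptoms with several plausible causes.

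The size is unknown. Under the assumed 20% and 45% rates, power goes from about 68% to between 62% and 38% for a 10% to 50% equal loss. It could rise to about 78% if the filter mostly removed background events. These figures show sensitivity to an unplanned filter and are not estimates for this trial.

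The stronger conclusion, that the arms cannot be compared on safety, goes beyond the documents. The change is worth making because it is cheap, the daily assessment already exists, and safety is a listed evaluation criterion.

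**What to change.** 1. Reconcile the summary, 9.1.1 and 9.1.2, and state explicitly whether AEs judged unrelated enter the TINALL database.
2. Change 9.1.2 so that at least nervous-system events (including sedation), respiratory events and gastrointestinal events found at the daily assessment are entered regardless of attribution, with CTCAE grade and blinded relatedness as data fields.
3. Add to section 11 a descriptive tabulation of these events by randomized arm, for all events and for those judged related. No formal test is needed.
4. Word the summary's safety sentence to match the scope chosen. If only the named groups are entered regardless of attribution, the sentence should say so.

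The cost is some additional data entry from an assessment already made each day, with some overlap with Total XVI reporting. IRB reporting rules do not change.
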